9.5 Stratification, Subgroup Analysis and Pooled Analysis

The stratification factors used in randomization, critical v. severe v. mild/moderate disease as defined above based on supplemental oxygen requirements, SpO2 status etc., will be accounted for in the efficacy analyses. The stratification factor may be deleted from the statistical model if the interaction is not significant at the 0.10 level. Efficacy data will be pooled across study sites for analysis, after visual inspection of summary results reveals similarity across study sites. Efficacy results may also be summarized within each randomization stratum for exploratory purposes.

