9.6 Efficacy Endpoint Analysis

The primary endpoint of time to viral clearance will be analyzed with the log-rank test for treatment difference and summarized using the Kaplan-Meier methodology as noted above. Viral load results from day of discharge as available will also be included in the analysis of viral clearance.

The key secondary endpoint of status of clinical recovery as measured by the study-specific 6-point ordinal scale at Day 15 will be analyzed using ordinal categorical data methods, since it is unlikely that linear differences exist between the elements of the scale (for example, a 1-point difference in magnitude may not apply to each increment on the scale). As an exploratory analysis, sequential binary analysis will be performed, based on successive classification of a subject into categories of less than or greater/equal to each ordinal item on the scale. Longitudinal analysis of the 6-point scale over time on study will also be performed to investigate temporal patterns of improvement.

Time to event endpoints will be analyzed using similar methods as used for the primary endpoint; these will include time to: clinical recovery; defervescence; cough mild or absent; dyspnea mild or absent; SARS-CoV-2 RT-PCR negative in upper respiratory tract.

Categorical endpoints will be analyzed using categorical data analysis methods; continuous data will be analyzed using analysis of variance with treatment and strata as factors.

Missing efficacy data in a trial of hospitalized patients is generally unlikely, and great care will be taken at each study site to ensure that all outcome assessments are obtained as planned in this protocol. However, as treatment of COVID-19 subjects evolves, it is clear some subjects will be discharged from the hospital prior to Day 15. Subjects are asked to return for follow up visits on Days 29, 45 and 60. This requirement is presenting challenges for subjects and in order to ensure that in cases where the subject does not return for their follow up visits, an additional swabbing has been added on the day of hospital discharge (See Section 7.7). Should missing data occur for the primary endpoint, time to viral clearance, such patients will be included in the log-rank analysis as censored observations. Missing clinical outcome data will be evaluated using a variety of methods, including multiple imputation, worst-value assignment, and other methods, to be completely outlined in the statistical analysis plan.

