### 1.2.2. Randomization Methodology

Subjects will be evaluated for eligibility during Day 1, prior enrollment in the study or starting treatment. The randomization procedure will be performed centrally using the electronic data capture (EDC) system, IBM Clinical Development.

Approximately 50 subjects are planned to be randomized at a 1:1 ratio to receive either favipiravir + SOC or SOC alone. Randomization will be stratified by site and severity of illness at enrollment. Severity of illness at enrollment will be graded (i.e., critical disease, severe disease, or mild/moderate disease) as follows:

- Critical disease:
  - Requires supplemental oxygen delivered by non-rebreather mask or high-flow cannula, OR
  - Requires use of invasive or non-invasive ventilation, OR
  - Requires treatment in an intensive care unit, use of vasopressors, extracorporeal life support (i.e., extracorporeal membrane oxygenation [ECMO]).
- Severe disease:
  - Evidence of pneumonia on chest x-ray or computed tomography (CT) scan, or chest auscultation (rales, crackles), OR
  - Peripheral capillary oxygen saturation ( $SpO_2$ )  $\leq$  93% on room air OR partial pressure of oxygen ( $PaO_2$ )/fraction of inspired oxygen ( $FiO_2$ )  $<$  300 mmHg, OR
  - Requires supplemental oxygen by nasal canula, simple face mask, or other similar oxygen delivery device.
- Mild/moderate disease:  $SpO_2 > 94\%$  and respiratory rate  $\leq 24$  breaths/min without supplemental oxygen

The randomization will target balance within stratum. This does not guarantee balance overall; however, utilizing a block size of 2, as well as with sufficient sample size within strata, balance will be approximately maintained while pooling across sites.

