#### **3.2. Efficacy Endpoints and Hypothesis Testing**

The primary efficacy endpoint is time to viral clearance by PCR, measured on Days 1, 3, 8, 11 (while hospitalized); and days 15 and 29 (if able to return to clinic or still hospitalized).

Contrary to what is included in the study protocol, the hierarchical testing of key secondary endpoints will not be performed. For more information please refer to [Section 5](#).

All analyses will be conducted at the two-sided alpha-level of 0.10. P-values for all analyses other than the primary efficacy endpoint will be presented for the purposes of ‘descriptive significance’ only.

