### **3.7. Adjustments for Covariates**

For the analyses of durations of supplemental oxygen, non-invasive/mechanical ventilation, Extracorporeal Membrane Oxygenation (ECMO), hospitalization, and ICU, baseline SpO2 level will act as a covariate in all analysis of covariance (ANCOVA) models. Disease severity, as defined in [Section 1.2.2](#), will be accounted for in all efficacy analyses. Other factors may be accounted for if deemed relevant.

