### **4.3. Efficacy Evaluation**

#### **4.3.1. Analysis of the Primary Efficacy Endpoint**

The primary endpoint of time to viral clearance will be analyzed with the log-rank test for treatment difference based on a two-sided alpha-level of 0.10 and summarized using Kaplan-Meier methodology. The time to viral clearance (in days) is defined as the time of Negative or Lower Limit of Quantification (LLOQ) results (without any quantitative results after that) as measured by PCR for SARS-CoV-2 via scheduled nasopharyngeal and oropharyngeal swab samples minus the date of first dose + 1.

Subjects who have no evidence of viral clearance will be censored at the time of the last PCR measurement with the following conditions:

- Patients whose symptoms worsen (defined as an increase of  $\geq 1$  point on the 6-point Ordinal Scale from baseline) on the day of the last PCR measurement, or who die will be censored at Day 29,
- Patients who are lost to follow-up will be censored on the day of the last PCR measurement.

The median time to viral clearance will be estimated based on the Kaplan-Meier estimator; additional summary statistics will be presented, including the 25th and 75th percentiles, 90% CIs (the log-log transformation) on the median and other percentiles and proportion of censored subjects. Viral clearance rates at Days 3, 8, 11, 15, and 29 will also be presented.

The analysis of the primary efficacy endpoint will be done using the ITT population.

The primary analysis will be supplemented with a sensitivity analysis, using a stratified log-rank test, where the treatment difference based on a two-sided alpha-level of 0.10 will be summarized and stratified by disease severity.

The analysis will also be repeated by the dexamethasone usage subgroup, where patients will be categorized as having received dexamethasone if they received it at any time prior to the last viral clearance assessment.

Kaplan-Meier curves will be provided for the overall ITT population. By-subject data listings of viral clearance data will also be provided.

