**Table 4-1 Normalization and Alleviation Criteria**

| Parameter         | Criteria   |
|-------------------|--|
| Fever             | $\leq 37.2$ °C   |
| Respiratory Rate  | $\leq 24$ breaths/minute on room air   |
| Oxygen Saturation | SpO 2 > 94% on room air   |
| Cough             | Mild or absent on a subject-reported scale of severe, moderate, mild, absent |

Subjects with no evidence of clinical recovery will be censored at last assessment of the parameter that is not be recovered. The censoring rules as provided in Section 4.3.1 will also be employed. In addition, if a subject achieves TTCR and then discontinues from the study during the 72 hour confirmation period, it will be censored at the discontinuation. If a subject achieves TTCR and then discharge, it will be confirmed as recovered at the time of achieving TTCR.

The difference between treatment groups will be analyzed using a log-rank test at the two-sided alpha level of 0.10, where the p-value will be presented for descriptive purposes (and using a stratified log-rank test by disease severity as a sensitivity analysis).

Analyses of TTCR will be done on the ITT population. Only patients with at least one abnormal result (among the four symptoms listed in Table 4-1) at baseline (or within 72 hours post baseline) will be included in the analysis.

Kaplan-Meier curves will be provided for the overall ITT population. By-subject data listings will also be provided.

In addition, the analysis will be performed with stratification by disease severity.

The analysis will also be repeated by the dexamethasone usage subgroup, where patients will be categorized as having received dexamethasone if they received it at any time prior to the last assessments of normalization and alleviation criteria.

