## **5. CHANGES TO PLANNED ANALYSES**

The following are changes between the protocol-defined statistical analyses and those presented in this statistical analysis plan:

- The hierarchical testing of the key secondary endpoints has been removed, given that this study is a Proof of Concept study that is not meant to act as a pivotal or confirmatory study for marketing authorization.

All changes from procedures outlined in the protocol and procedures outlined in this SAP will be summarized in the study report. Decisions to deviate from planned analyses will be documented at the time they are made.

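### The primary log-rank test ignores the severity stratum used in randomization, although SAP 3.7 says severity is accounted for in every efficacy analysis

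*SAP*

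**What the plan says.** On randomization, SAP 1.2.2 states: "Randomization will be stratified by site and severity of illness at enrollment". Severity has three levels (critical, severe, mild/moderate), and the block size is 2.

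On adjustment, SAP 3.7 says disease severity "will be accounted for in all efficacy analyses". It lists no exception.

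On the primary test, SAP 4.3.1 specifies a log-rank test at two-sided 0.10 and names no strata. It then adds: "The primary analysis will be supplemented with a sensitivity analysis, using a stratified log-rank test", with disease severity as the stratum and the same alpha. The word unstratified does not appear, but the primary test must be unstratified because the stratified one is listed separately as its supplement. SAP 4.3.2.2 uses the same order for time to clinical recovery (TTCR): a log-rank as the main test, "using a stratified log-rank test by disease severity as a sensitivity analysis".

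The protocol has the same split. Section 9.5 says the stratification factors enter the efficacy analyses, then adds: "The stratification factor may be deleted from the statistical model if the interaction is not significant at the 0.10 level". Section 9.6 says the primary endpoint "will be analyzed with the log-rank test for treatment difference and summarized using the Kaplan-Meier methodology as noted above", without strata.

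SAP Section 5 lists one change from the protocol: "The hierarchical testing of the key secondary endpoints has been removed".

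**The concern.** Two SAP sections give different answers to whether the primary p-value is adjusted for severity. That p-value decides the trial. Protocol 9.1 makes proof of concept depend on a significant effect on time to viral clearance, and SAP 3.2 says "P-values for all analyses other than the primary efficacy endpoint will be presented for the purposes of" descriptive significance only. With two tests at the same alpha and two sections pointing different ways, a split result would be open to dispute.

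There is also an efficiency question. Stratified allocation balances severity between the arms. An unstratified log-rank does not use that balance: its variance still allows for chance imbalance in severity, which the design has largely removed. If severity predicts clearance, the test therefore rejects too rarely under the null. Pooling unlike strata also dilutes the treatment hazard ratio. Both effects cost power in a trial of 50 sized for 90%.

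The deletion rule in protocol 9.5 does not resolve this. A missing treatment-by-severity interaction does not show that severity is unrelated to outcome, so it is no reason to drop a prognostic stratum. The SAP does not carry the rule forward, and 4.3.1 does not depend on it.

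**Working it through.** **1. The plan's own figure.** Inputs from protocol 9.2 and SAP 3.1: medians of 4 and 11 days, two-sided alpha 0.10, power 90%, 15 days of observation, 25 per arm. With exponential times:

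- Ratio of medians 4/11 = 0.364; treatment hazard ratio for clearance 11/4 = 2.75.
- Probability of clearance by Day 15: 1 - 2^(-15/4) = 0.926 and 1 - 2^(-15/11) = 0.611; mean 0.769.
- Freedman events: (1.645 + 1.282)² × [(1 + 0.364)/(1 - 0.364)]² = 39.3; N = 39.3/0.769 = 51.2.
- Exponential-rate formula with fixed follow-up: 25.3 per arm.
- Schoenfeld: 34 events, N about 44 to 45.

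The stated 50 agrees with the first two. At N = 50 (38.4 expected events) power is 89.4% by Freedman and 93.2% by Schoenfeld. None of these formulas has a term for strata, so the choice of test leaves N unchanged.

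**2. Simulation set-up.** From the documents: N = 50, 1:1 allocation, about 8 sites, permuted blocks of 2 within site by severity, SOC median 11 days (placed in the severe stratum), treatment hazard ratio 2.75, swabs on Days 3, 8, 11 and 15, two-sided 0.10. Assumed, because the documents are silent: the stratum mix, the clearance-rate ratio per severity level (slower with worse disease), exponential times, and correct classification of severity. There were 5,000 trials per cell, with a Monte Carlo standard error of 0.4 to 0.7 points on each power.

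**3. Power, unstratified / stratified (%).** Mix is mild-moderate/severe/critical; columns are the severity rate ratio per level.

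| Mix | 1 | 1.5 | 2 | 3 |
|---|---|---|---|---|
| 33/33/33 | 92.5 / 91.8 | 89.8 / 90.6 | 83.8 / 89.9 | 68.2 / 86.9 |
| 30/50/20 | 93.1 / 92.3 | 90.8 / 91.6 | 86.8 / 91.0 | 77.1 / 89.6 |
| 20/60/20 | 92.9 / 91.7 | 91.4 / 91.4 | 87.3 / 89.7 | 80.7 / 89.5 |
| 10/80/10 | 92.1 / 91.3 | 91.5 / 91.2 | 90.5 / 91.2 | 88.2 / 91.5 |
| 5/75/20 | 92.9 / 92.0 | 91.1 / 90.8 | 89.3 / 90.6 | 85.5 / 89.8 |
| 5/90/5 | 92.7 / 91.9 | 92.7 / 92.1 | 92.0 / 92.2 | 90.0 / 91.4 |

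Stratified minus unstratified, by column: -0.7 to -1.2; -0.6 to +0.8; +0.2 to +6.1; +1.4 to +18.7 points. With exact event times and no severity effect, the figures are 92.6 / 91.2 (30/50/20) and 93.6 / 92.3 (10/80/10), a cost of 1.4 and 1.3 points.

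**4. Type I error at ratio 3, nominal 10%.** In the same mix order, unstratified: 5.4, 7.2, 7.6, 9.1, 9.7, 9.9%. Stratified: 9.6, 10.4, 10.3, 9.9, 10.4, 9.9%.

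**5. Separate simulation.** 1,500 trials per cell, mix 25/50/25, blocks of 2 within severity only, continuous observation to Day 15. Unstratified v stratified power was 93.1% v 91.4% at ratio 1, 91.9% v 92.6% at 1.5, 87.7% v 91.5% at 2 and 80.9% v 91.4% at 3. The two tests disagreed on significance in about 3%, 3%, 6% and 12% of trials. With swab-day detection at ratio 3, power was 77.3% v 88.5%.

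**6. Sparse strata.** The chance that some stratum holds 3 or fewer subjects is about 1% or less at 20/60/20 or more even mixes, 45% at 10/80/10 and 76% at 5/75/20. The chance that a stratum contains one arm only is about 18% at 10/80/10 and 36% at 5/75/20.

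**The case against.** The strongest reply is that the primary test is clear and follows the protocol. Protocol 9.2 and 9.6 both name a plain log-rank, a specific section normally governs a general sentence, and the stratified result will be reported anyway. The unstratified test errs only on the conservative side, and the study is a proof of concept. All of this stands as to validity. Agreement with protocol 9.6 also means that Section 5 had no change from 9.6 to record. But 4.3.1 still departs from protocol 9.5 and from the literal wording of SAP 3.7, and a supplementary test does not adjust the p-value that decides the trial.

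The second reply is that the gain rests on assumptions. The 18.7-point figure needs an even mix and a ratio of 3 per level, which is ninefold (3²) from mild-moderate to critical. Severe disease is broadly defined and ventilated subjects are excluded, so most subjects may fall in that stratum. At 10/80/10 and 5/90/5 the gain is only 0.2 to 0.7 points at ratio 2 and 1.4 to 3.3 at ratio 3. The severity definitions also overlap (SpO2 96% with pneumonia meets two levels) and leave a gap (SpO2 94% without pneumonia or oxygen meets none). With an assumed 20% misclassification, the gain at ratio 3 falls to about 1 point at 10/80/10 and 5/75/20, 7 at 30/50/20 and 12 at 33/33/33. This too stands, and it is why the size is given as a range. It does not reverse the direction of the trade.

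The third reply is that sparse strata make the fix more than a change of wording. A rule is needed, but a one-arm stratum adds nothing to the numerator or the variance of a stratified log-rank, so the test remains defined.

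**Conclusion.** The concern holds. SAP 3.7 and 4.3.1 conflict as written, protocol 9.5 and 9.6 conflict in the same way, and no exception or reason is given. The consequence is possible loss of power and doubt over which p-value is adjusted. It is not an inflated false-positive rate.

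The trade favors stratifying. Across both simulations the cost is 0.7 to 1.7 points of power if severity does not matter. The gain is negligible at a ratio of 1.5 per level, up to about 6 points at 2, and between about 1 and 19 points at 3, with the larger gains in more even mixes. These figures rest on an assumed severity effect, an assumed mix, exponential times and correct classification, so confidence in the size is medium. The change should be made, but the trial is interpretable without it. For TTCR and the other time-to-event endpoints the p-values are descriptive and the consequence is small.

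**What to change.** - In SAP 4.3.1, make the log-rank stratified by the randomized severity factor the primary test, with the unstratified log-rank as the sensitivity analysis. Stratify by severity only: site by severity would be too sparse with 50 subjects.
- State in advance how a sparse stratum is handled. For example, merge an empty or one-arm stratum with the adjacent severity level, decided from randomization counts before any PCR outcome is seen.
- Use the same order for TTCR and the other time-to-event endpoints.
- Remove the interaction-based deletion rule from protocol 9.5, and align protocol 9.5 and 9.6 with SAP 3.7 and 4.3.1.
- If the sponsor keeps the unstratified test as primary, SAP 3.7 should name it as an exception and give the reason.

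The sample size stays at 50 and no new data are needed. The cost is the wording, one merging rule, and about 1 point of power (allow up to about 2) if severity proves not to be prognostic.

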#### 4.3.2. Analysis of Secondary Efficacy Endpoints

##### 4.3.2.1. Analysis of Clinical Status via the Study-Specific 6-point Ordinal Scale

The first secondary endpoint of clinical status as measured by the study-specific 6-point ordinal scale at Day 15 will be analyzed by fitting a cumulative odds model, using the most appropriate approach. Clinical status will be modelled as the dependent variable (ordered from 1 to 6, as defined in [Section 1.2.6.1](#)), and treatment group and disease severity as independent variables; other factors may be added for exploratory purposes. Subjects with missing Day 15 data will have their clinical status imputed in the following manner:

- 1) If patients were discharged prior to Day 15, then their clinical status will be imputed to 'Not Hospitalized' at Day 15
- 2) If patients died prior to Day 15, then their clinical status will be imputed to 'Death' at Day 15
- 3) If there is no evidence of hospital discharge or death, clinical status at Day 15 will be imputed using the multiple imputation method described in [Section 3.10.1](#)

The odds ratios and their 90% CI will be provided. As described in [Section 3.2](#), a test at the two-sided alpha level of 0.10 will be performed for descriptive purposes.

Longitudinal analysis of the 6-point scale over time at each visit will be performed in a similar manner. Clinical status will be modelled as the dependent variable and treatment group, disease severity, visit, and the visit/treatment group interaction term as independent variables. The overall treatment odds ratio and their 90% CI will be provided, along with by-visit odds ratios and 90% CI.

Analyses using the study-specific 6-point scale will be done using the ITT population.

The analysis will also be repeated by the dexamethasone usage subgroup, where patients will be categorized as having received dexamethasone if they received it at any time prior the Day 15 analysis visit assessment.

Stacked bar charts over time will be generated to graphically display the proportion of patients in each level of the 6-point scale by treatment group for the ITT population.

By-subject data listings will be provided.

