- 12. Is on another antiviral or is participating in a clinical trial for the treatment of COVID-19.
- 13. Is on a ventilator at the time of study entry.
- 14. Is deemed by the Investigator to be ineligible for any reason.

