7.1 Day 1 (PRE-DOSE)

- Obtain informed consent.
- Verify eligibility per the inclusion and exclusion criteria. (See Sections 5.1 and 5.2)
 - o Review and record medical history, including tobacco use, to ensure there are no exclusionary illnesses.
 - Review and record concomitant medications for possible prohibited medications. (See Section 6.7)
- If subject is female of child-bearing potential and meets inclusion criteria 4.c, obtain urine or blood pregnancy test and proceed it result is negative.
- Measure and record vital signs (BP, HR, Temp, Resp).
 - **NOTE:** vital signs to be recorded and entered in the EDC every day while subject is in the hospital and on return study visits after discharge.
- Perform Physical exam (may be done by the Principal Investigator or their designee)
- Assess and record baseline clinical status according to the following study-specific 6-point scale:
 - 1. Not hospitalized
 - 2. Hospitalized, not requiring supplemental oxygen
 - 3. Hospitalized, requiring supplemental oxygen
 - 4. Hospitalized, on non-invasive ventilation or high flow oxygen devices
 - 5. Hospitalized, on invasive mechanical ventilation or ECMO

6. Death

NOTE: Clinical Status to be recorded and entered in the EDC every day while subject is in the hospital and on return study visits after discharge.

- Assess and record NEWS2 (See charts by clicking this link: https://www.rcplondon.ac.uk/projects/outputs/national-early-warning-score-news-2
 - **NOTE:** NEWS2 assessment to be recorded and entered in the EDC every day while subject is in the hospital and on return study visits after discharge.
- Assess and record ECOG Performance Status and Study-specific Symptom Status (see Appendix A).
 - **NOTE:** ECOG Performance Status and Study-specific Symptom Status to be collected and recorded every day while the subject is in the hospital and on return study visits after discharge.
- Collect nasopharyngeal and oropharyngeal swabs for virologic testing. (See Virology Laboratory Manual.)
- Collect blood samples for:
 - o Antibodies to SARS-CoV-2.
 - o Hematology and clinical chemistry laboratory analyses
- Collect and record SpO2 by Finger Sensor
 - **NOTE:** SpO2 to be recorded and entered in the EDC every day while subject is in the hospital and on return study visits after discharge.
- Perform subject randomization (via EDC) to establish treatment arm (favipiravir + SOC or SOC alone).

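### The cumulative-odds models for the 6-point scale adjust for disease severity but do not pre-specify the baseline score, so chance imbalance within severity strata is left unadjusted

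*SAP*

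**What the plan says.** SAP 4.3.2.1 fits a cumulative-odds model to Day 15 clinical status with "treatment group and disease severity as independent variables". The longitudinal version adds visit and a visit-by-treatment term. Beyond these, the section says only that "other factors may be added for exploratory purposes". SAP 3.7 keeps disease severity in every efficacy analysis and adds: "Other factors may be accounted for if deemed relevant".

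The baseline score is available. The Day 1 pre-dose list in Protocol 7.1 includes "Assess and record baseline clinical status according to the following study-specific 6-point scale", placed ahead of the randomization step.

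Severity is a randomization stratum together with site (SAP 1.2.2). One route into the critical stratum is "Requires supplemental oxygen delivered by non-rebreather mask or high-flow cannula, OR" and another is intensive-care treatment. One route into the severe stratum is "Requires supplemental oxygen by nasal canula, simple face mask, or other similar oxygen delivery device", but pneumonia on imaging or auscultation is enough alone.

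The baseline score is used in two other places. It enters the multiple-imputation model (SAP 3.10.1), and it is the reference for an improved/not-improved sensitivity analysis (SAP 4.3.2.1.1). The Day 15 test is labelled descriptive.

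**The concern.** Severity and the baseline score measure nearly the same thing, but not exactly. Two severe subjects can start at different levels of the scale on which they are later scored: one on room air with pneumonia (score 2), one on nasal oxygen (score 3). In the critical stratum, a subject admitted to intensive care for another reason, or on a non-rebreather mask, need not be at score 4. Randomization balances the strata, not the mix of scores inside them. With about 25 subjects per arm, that mix can differ between arms by chance and move the odds ratio.

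The SAP adjusts for a baseline measurement elsewhere: baseline viral load in the viral-load repeated-measures model (4.3.2.9), and baseline SpO2 in the duration ANCOVAs (3.7). The first secondary endpoint does not get its own baseline.

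The estimate matters more than the test here. A stated objective is to judge whether the Day 15 scale could be the primary clinical endpoint of a later blinded study, so the odds ratio is likely to be carried forward.

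**Working it through.** **The plan's own figure.** No size or power is stated for the ordinal model. The stated total of 50 is for the log-rank test and reproduces:

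- Medians of 4 and 11 days give a rate ratio of 11/4 = 2.75.
- Clearance by Day 15 is 1 − 2^(−15/4) = 0.926 and 1 − 2^(−15/11) = 0.611, mean 0.769.
- Freedman's formula at two-sided 0.10 and 90% power gives N = 51.2 (89.4% power at 50). Lachin's formula gives 25.3 per arm.

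This point does not affect that figure.

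**Possible baseline range.** Subjects are hospitalized and alive, so not 1 or 6. An exclusion criterion reads "Is on a ventilator at the time of study entry", which removes score 5. That leaves scores 2 to 4. Mild/moderate disease means no supplemental oxygen, hence score 2. Critical disease is mostly score 4. The main residual is score 2 versus 3 in the severe stratum.

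**Size of a typical imbalance.** The documents give none of these inputs, so they are assumptions: 65% severe, of whom 30% are at score 2 and 70% at score 3, and a log-odds slope of 1.2 per level.

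- Severe subjects per arm: 0.65 × 25 = 16.25.
- SD of the arm difference in the share at score 3: √(2 × 0.3 × 0.7 / 16.25) = 0.16.
- Shift in the overall log odds ratio: 0.65 × 0.16 × 1.2 = 0.125, a factor of exp(0.125) = 1.13.

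Range, holding 65% severe:

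- Low end, 20/80 split and slope ln 2: 0.65 × √(0.32/16.25) × 0.693 = 0.063, a factor of 1.07.
- High end, 50/50 split and slope ln 4: 0.65 × √(0.50/16.25) × 1.386 = 0.158, a factor of 1.17.

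**Simulation of the cumulative-odds model.** Settings: n = 50; randomization stratified by severity (sites ignored); assumed strata 15/65/20% mild/severe/critical; 50% or 80% of severe subjects at score 3; baseline odds ratio 2 or 4 per point; assumed Day 15 cutpoints; likelihood-ratio test at two-sided 0.10; 1,464 to 1,500 usable runs per scenario. Mild subjects were all at score 2 and critical subjects all at score 4.

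| Quantity (range over scenarios) | True OR 1 | True OR 1/3 |
|---|---|---|
| Rejection rate, severity only | 10.7–12.7% | 47.9–52.1% |
| Rejection rate, severity + score | 11.5–12.5% | 49.3–52.1% |
| SD of log OR, severity only | 0.66–0.74 | 0.80–0.84 |
| SD of log OR, severity + score | 0.67–0.79 | 0.82–0.87 |
| Chance of a gap of 20 points or more in the share at score 3 | 16–26% | 16–28% |
| Shift in log OR from a 20-point gap, severity only | 0.09–0.18 | 0.09–0.14 |
| Same, severity + score | −0.01 to 0.04 | −0.02 to 0.02 |

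The 20-point shift agrees with direct arithmetic: 0.65 × 0.20 × ln 2 = 0.09 and 0.65 × 0.20 × ln 4 = 0.18, or factors of about 1.1 to 1.2. Adding the score removes most of it. Power gains within scenarios run from 0 to 1.4 points. A separate rank-ANCOVA approximation (4,000 trials per scenario, OR 3 and 4) gave 0 to 3 points, for example 55% to 58% at OR 4, and a 1-point loss when the score carries no information.

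**Against the noise.** 0.125/0.84 = 0.15 and 0.125/0.66 = 0.19, so a one-SD imbalance is 15 to 19% of one SD of the estimate, or about 2 to 4% of its variance.

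**The case against.** The case for leaving the model alone is substantial.

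- **Severity already does most of the work.** It is stratified on, is in the model, and is defined largely by oxygen support. A reader might infer that baseline imbalance goes wholly uncorrected. It does not; only the within-stratum part does. This stands.
- **The baseline score is not shown to be the best predictor.** A reader might infer that the strongest available predictor is being ignored. No figure in the documents ranks predictors, and age, SpO2 and NEWS2 are also available at baseline. This stands.
- **There is no bias.** A reader might infer a distorted treatment effect or excess false positives. Under randomization this is chance variation that the confidence interval already reflects. Null rejection rates show no systematic difference between the models; both sit slightly above 10%. This stands.
- **Little depends on it.** Proof of concept rests on viral clearance, and the SAP removed hierarchical testing of secondary endpoints. This stands as to testing, less so for an estimate meant to inform a later trial.
- **The odds ratio is non-collapsible.** Adding a covariate changes the quantity estimated, so not all movement is correction. In the simulation at OR 1/3 the mean log odds ratio moved 0.02 to 0.06 further from zero, and its SD did not fall. This stands and belongs in the SAP text.
- **The plan already permits or uses the score.** This stands only in part. The optional-factor wording names nothing, and in an open-label trial covariates are best fixed beforehand. The sensitivity analysis only dichotomizes against baseline and drops discharged and deceased subjects from later timepoints. Tabulating respiratory assistance at baseline (SAP 4.2) would show an imbalance, not adjust for it. None of these gives a pre-specified, baseline-adjusted Day 15 odds ratio.

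**Conclusion.** The point holds as a minor refinement. The Day 15 and longitudinal models omit a baseline value that the trial already collects, and chance imbalance in it within severity strata, chiefly score 2 versus 3 among severe subjects, is not adjusted for.

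The gain is protection of the estimate against an unlucky draw, not power. All magnitudes rest on assumed strata mix, score split and slope. No magnitude was worked out for mixing in the critical stratum or for the longitudinal model.

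The point would weigh more if severity left the model. Protocol 9.5 allows that: "The stratification factor may be deleted from the statistical model if the interaction is not significant at the 0.10 level". SAP 3.7 retains severity throughout. These two texts should be reconciled. So should the listing of invasive ventilation in the critical stratum and the exclusion of ventilated subjects, since that determines which baseline scores can occur.

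**What to change.** In SAP 4.3.2.1, name the baseline 6-point score as one linear covariate alongside severity, in both the Day 15 and the longitudinal model.

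Define it as the Day 1 value recorded before randomization in both arms. SAP 3.5 lets the SOC baseline be the measurement closest to randomization on either side, and a covariate should not be measured after allocation in an open-label trial.

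State that the odds ratio is then conditional on baseline score as well as severity. If the sponsor prefers to keep the present model as the main one, the baseline-adjusted model should at least be a named sensitivity analysis.

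Cost: one model term, one degree of freedom and no new data, with a possible 1-point loss of power if the score proves uninformative.
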